### **Introduction**

Acute pancreatitis (AP) is a acute inflammatory disease of the pancreas. The incidence of AP ranges from 5 to 30 cases per 100,000, with an overall case fatality rate of 5%. Approximately 80% cases of AP are mild and self-limited, and about 20% of patients suffer a severe disease course with persistent organ failure and/or infected pancreatic necrosis (IPN), with a mortality risk as high as 20~30%.

Gastrointestinal tract is considered not only as a target organ during systemin inflammatory response syndrome (SIRS) and multiple organ dysfunction syndrome (MODS), but also a “motor organ” of gut-derived infection. Gastrointestinal dysfunction has been proven to be associated with adverse outcomes in AP.

Although the mechanisms underlying gastrointestinal dysfunction in the early phase of AP is complicated, early gastrointestinal barrier dysfunction was considered to be the main cause. Gastrointestinal microbiota dysbiosis induces the injury of biologic barrier, which plays a key role in the pathogenic of gut-driven infection. Therefore, the maintenance of gastrointestinal microecology balance may be an effective method in treating gastrointestinal dysfunction, preventing gut-driven infection and improve clinical outcomes in AP.

Probiotics, as an adjunct to enteral nutrition, has long been studied as a measure to improve intestinal barrier dysfunction and prevent secondary infection in AP. Several clinical studies have assessed the effect of probiotics prophylaxis with contradictory results, and significant heterogeneity was noted between the trials with regard to the

type, dose and treatment duration of probiotics. A multicenter, double-blind, placebo-controlled trial have failed to show a beneficial effect of probiotic prophylaxis on the occurrence of infectious complications, and mortality in the probiotics group was about twice as high as in the placebo group. The current data are not sufficient to draw a conclusion regarding the effects of probiotics on patients with predicted severe acute pancreatitis (SAP). Consequently, there is a clear need for other innovative strategies.

Worldwide, interest in fecal microbiota transplantation (FMT) as an 'ecological' therapy for several diseases is growing rapidly. FMT presents another and more comprehensive approach to microbiota restoration. FMT consists of administering fecal material from a healthy donor into the intestinal tract of a patient. Unlike the few bacterial strains included in probiotics, FMT stool includes practically all the bacteria, viruses, eukaryotes, and metabolites from the healthy donor. In recurrent *Clostridium difficile* infections, FMT has shown excellent effects by restoring intestinal microbiota balance. Several cases reported that patients with SIRS and severe diarrhea of unclear etiology persistently unresponsive to broad-spectrum antibiotics rapidly improved with FMT in the Intensive Care Unit (ICU). The improvements in clinical parameters were also associated with shifts in the recipients' microbiota patterns toward that of the donors', further attributing the patients' recovery to FMT. FMT could therefore theoretically be a possible treatment for AP patients with gastrointestinal dysfunction. No randomized controlled study evaluating FMT in AP patients has been published to date.

Here, we performed the randomized, single-blind, parallel-group, placebo-controlled study to clarify the effects of FMT on gastrointestinal dysfunction and infectious complications, as well as gut microbiota in patients with AP.

## Methods

This is a randomized, single-blind, parallel-group, placebo-control, single-center study in consecutive adults diagnosed with acute pancreatitis complicated with gastrointestinal failure in the setting of ICU. Eligible participants were randomized 1:1 to receive fecal transplant or normal saline via a nasoduodenal tube for twice (once

every two days). The primary end point the recovery of gastrointestinal dysfunction assessed by gastrointestinal failure (GIF) score one week after intervention.

### **Trial organization, committees and boards**

The designer of this trial is the First Affiliated Hospital of Nanchang University, China (<http://www.cdyfy.com/>). This study was investigator-initiated and investigator-driven and done in accordance with the principles of the Revised Declaration of Helsinki.

The study protocol was approved by the institutional review boards of the First Affiliated Hospital of Nanchang University (approval No, 2014 [32]). Written informed consent was obtained from all participants or their legal representatives. All physicians involved in the study will repetitively be asked to report any potential adverse events. All possible adverse events will be listed and reported to the institutional review boards of the First Affiliated Hospital of Nanchang University.

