### **Primary Endpoint**

The primary end point was the recovery of gastrointestinal dysfunction assessed by GIF score one week after intervention. The normal gastrointestinal function assessed by GIF score means enteral feeding >50% of calculated needs, without FI and IAH. FI was defined when applied enteral feeding appeared to be unsuccessful

and had to be discontinued because of repeated or profuse vomiting, high gastric residuals, ileus, severe diarrhea, abdominal pain, or distension. FI should not be considered as present if enteral feeding is electively not prescribed or is withheld/interrupted due to procedures. IAP was measured by the standardized methodology (preferably the transvesical method, with a maximal instillation of 25 cc of saline in the supine position, measured at the end of expiration, with zeroing done at the level of the midaxillary line). IAH was present if the IAP was found to be 12 mmHg or higher, as confirmed by at least two measurements taken 1-6 h apart.

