## **Intervention**

All participants underwent interventions one day after allocation. In the FMT group,

participants received 200 mL fresh donor feces for twice (once every two days). In the control group, participants received 200 mL normal saline. The fecal transplant or normal saline were drawn on 50 mL sterile sealed syringe and infused into each patients via a nasoduodenal tube, which was inserted into distal duodenum by endoscopy. The procedure was performed within 5 min at the bedside of pancreatic intensive care unit by a researcher who were not involved in the clinical performance of the trial. The patients were blinded to the identity of the intervention that they were receiving because either FMT or placebo were stored on a sealed syringe. Before FMT or normal saline, Laxative was stopped for at least one hour to retain stool. To assure maximum delivery and colonization of these fecal transplant, first we assured a at least 4-hour gap between study medication and antibiotics (if prescribed) or laxative. No probiotics or lactulose was used during hospitalization. Considering the feasibility, we altered the protocol (after registration at ClinicalTrials.gov, but before enrolment of participants) to implement FMT or normal saline via a nasoduodenal tube instead of via retention enema.

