### **Follow up**

Patients are followed during their hospital stay. There is one follow-up visit, 6 months after discharge by clinical visit or telephone visit, to assess readmission, mortality and adverse events.

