### **Statistical analysis**

Quantitative variables are presented as medians (ranges) or means  $\pm$  standard deviations and were analysed using the Mann-Whitney U test or t-test as appropriate. Categorical variables are reported as absolute numbers and proportions and were tested by the chi-square test or Fisher's exact test as appropriate. The differences between outcomes for matching data were tested with the paired t test or Wilcoxon signed-rank test as appropriate. We estimated relative risks (RRs) and 95% confidence intervals (CIs) for primary outcomes and secondary outcomes. A two-tailed P value  $<0.05$  was considered statistically significant. Data were analyzed using SPSS software (v17.0; SPSS Inc., Chicago, IL, USA).

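### Adverse event collection is prompted but unstructured, with no post-infusion window and no stated by-arm summary, so transient non-infectious events and readmission may go unreported by arm

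*Combined protocol and SAP*

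**What the plan says.** All references are to the combined protocol and SAP.

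- **Collection.** Trial organization, committees and boards: "All physicians involved in the study will repetitively be asked to report any potential adverse events". No event terms, grading or timing are given.
- **Handling.** Same section: "All possible adverse events will be listed and reported to the institutional review boards of the First Affiliated Hospital of Nanchang University". No summary by arm is mentioned.
- **Exposure.** Intervention: in the FMT arm "participants received 200 mL fresh donor feces for twice (once every two days"; the control arm receives the same volume of saline, and Methods gives both arms two administrations. On delivery: "The procedure was performed within 5 min at the bedside of pancreatic intensive care unit". No observation period or form after an infusion is described.
- **Follow-up.** Follow up: "Patients are followed during their hospital stay", and then "There is one follow-up visit, 6 months after discharge by clinical visit or telephone visit, to assess readmission, mortality and adverse events".
- **Endpoints.** Primary Endpoint: "The primary end point was the recovery of gastrointestinal dysfunction assessed by GIF score one week after intervention". Secondary endpoints cover infectious complications, organ failure, gut barrier and inflammatory markers, length of stay and death. Neither adverse events nor readmission is listed.
- **Analysis.** Statistical analysis: "We estimated relative risks (RRs) and 95% confidence intervals (CIs) for primary outcomes and secondary outcomes". A more general sentence in that section says categorical variables are given as counts and percentages and tested with chi-square or Fisher's exact test. It does not name the variables.

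**The concern.** By the Inclusion criteria, every patient enters with abdominal distension and intra-abdominal hypertension, and then receives two rapid infusions into the duodenum. The events one would first look for after such a procedure are vomiting, pain, more distension, diarrhoea and a rise in intra-abdominal pressure. In the planned analysis these count through the gastrointestinal failure (GIF) score at one week. An event that follows an infusion and has gone by one week reaches the record only if a physician mentions it when asked, and reaches the results only if someone decides to tabulate it. Readmission at 6 months is collected, but no analysis is named for it.

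The Introduction states that no randomised trial of FMT in acute pancreatitis has been published. A table of how the infusions were tolerated in each arm is therefore a basic result of this study. As written, the plan does not assure it.

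**Working it through.** **1. Where each kind of event would appear in the results**

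| Event | Planned place in the results |
|---|---|
| Infected necrosis, infected ascites, bacteraemia, pneumonia, urinary infection | Secondary endpoint, relative risk with 95% CI; not limited to one week |
| Organ failure (modified Marshall score of 2 or more) | Same; persistence beyond 48 hours is defined separately, so short-lived organ failure is not ruled out |
| Death | Same |
| Feeding intolerance or intra-abdominal hypertension at one week | Part of the primary endpoint |
| Vomiting, pain, distension, diarrhoea, bleeding or pressure rise that settles before one week | List to the review board; no by-arm summary stated |
| Readmission by 6 months | Collected; no analysis stated |

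The gap is the last two rows.

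**2. The plan's own figure.** The documents give no adverse event rate and no safety sample size. The only figure that matters here is 30 per arm. Reading the 85% and 50% under Sample size as recovery rates, with two-sided alpha 0.05 and 80% power:

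n = (1.960 + 0.842)² × (0.85 × 0.15 + 0.50 × 0.50) / 0.35² = 24.19 per arm, against the stated 24.

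48 / (1 − 0.20) = 60 matches the enrolled total, so a 20% dropout allowance is implied. The point does not depend on this calculation.

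**3. What 30 per arm can show with complete collection**

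- Zero events in 30: exact two-sided 95% upper limit 1 − 0.025^(1/30) = 11.6%.
- Chance of at least one event in an arm, 1 − (1 − p)^30: 45% at p = 2%, 79% at 5%, 96% at 10%, 99.9% at 20%.

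**4. Assumed counts, to show the precision of a by-arm contrast**

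- 6/30 against 1/30: RR = 6.0; SE(log RR) = √(1/6 − 1/30 + 1/1 − 1/30) = 1.049; 95% CI 0.77 to 46.9; Fisher p = 0.10. Risk difference 5/30 = 16.7 percentage points.
- 8/30 against 2/30: RR = 4.0; SE = √(1/8 − 1/30 + 1/2 − 1/30) = 0.747; 95% CI 0.92 to 17.3; Fisher p = 0.08. Risk difference 6/30 = 20 percentage points.

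**5. Effect of incomplete capture.** Exact power of the two-sided Fisher test at 30 per arm is the sum of the binomial probabilities of all tables with p < 0.05. The last column assumes that half of the events are reported in both arms.

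| Assumed true rates | All events captured | Half captured |
|---|---|---|
| 20% v 5% | 24% | 4% |
| 30% v 10% | 37% | 9% |
| 40% v 10% | 71% | 24% |
| 50% v 10% | 91% | 44% |

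Testing is weak even with full capture, so the output should be descriptive. Incomplete capture weakens it further even when it is equal in both arms, which is the case for a structured form. All rates and the one-half capture fraction are assumptions.

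**The case against.** Four stronger readings are tempting, and the documents support none of them.

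- **That reports are unsolicited.** A reader might infer this from the missing form. The plan has physicians asked repeatedly, and adverse events are assessed again at the 6-month visit.
- **That adverse events are never compared by arm.** The sentence on relative risks names primary and secondary outcomes but does not say that nothing else is analysed, and the general sentence on categorical variables could cover adverse events and readmission. What can be said is that no such comparison is specified.
- **That acute harm is invisible.** Events are listed for the review board, and infection, organ failure and death are compared by arm without a one-week limit. The probiotic trial in the Introduction, with mortality about twice that on placebo, is no argument for this gap, because mortality is already an endpoint.
- **That without a window the arms cannot be contrasted.** Patients are randomised, both arms have the same infusion schedule and follow-up, and Randomization and masking states that investigators, patients and outcome assessors are masked. Background disease events balance in expectation. Unstructured capture lowers sensitivity; it does not make a contrast impossible.

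It is also fair to say that an extra descriptive table leaves the primary analysis untouched, that the case report forms mentioned under Data collection are not shown and may hold more than the text describes, and that a checklist requiring new pressure measurements would cost more than charting. The last objection is met by using recorded values only.

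What stands is that no event list, post-infusion window or by-arm safety summary appears, and readmission is not an endpoint.

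**Conclusion.** The point holds in a limited form. Transient events that are neither infectious nor organ failure and that settle before the one-week GIF assessment, together with 6-month readmission, have no assured place in the results by arm. How many events this concerns cannot be estimated from the documents, and the counts and rates in the working are illustrations only. Nothing here shows that harm occurred or that reporting would differ between arms. The change is worth making because it is cheap and because the same form and window in both arms give better capture, and less room for uneven ascertainment, than reports made when a physician happens to be asked. It does not affect the primary analysis. This rests on the text as published; if the case report forms already contain such a checklist, only the analysis half of the point remains.

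**What to change.** **Trial organization, committees and boards; Intervention.** Add a data-collection checklist, completed by masked staff over the same fixed window after each infusion in both arms. Items: vomiting, abdominal pain or distension, severe diarrhoea, gastrointestinal bleeding, intestinal fistula, and any intra-abdominal pressure values already charted. No extra measurement is required. The trial team should set the window length in advance; the infusions are two days apart, so a window shorter than that keeps the two from overlapping. Because pressure is taken only as charted, report how many patients per arm had a value.

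**Secondary endpoints; Statistical analysis.** List the checklist events, all adverse events and 6-month readmission as descriptive safety outcomes. For each, give the number of patients with at least one event per arm and the risk difference with an exact 95% CI, naming the exact method, and make no significance claim. For readmission, state the denominator, since patients who die before discharge cannot be readmitted.

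Much of the plan is written in the past tense. If collection is already complete, the by-arm table can still be made from the adverse event list and the 6-month data, with a note that capture was unstructured.

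**Cost.** One form of extra data entry, a longer event listing and one extra table. Intervals will be wide at 30 per arm, and a clean arm will still be compatible with a true rate of up to 11.6%.

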### **Study population**

Adult patients with AP were recruited from the ICU, Department of Gastroenterology, First Affiliated Hospital of Nanchang University. The diagnosis of AP requires two of the following three features: 1) upper abdominal pain; 2) serum lipase or amylase activity at least three times greater than the upper limit of normal; and 3) characteristic findings of AP on contrast-enhanced computed tomography (CECT), magnetic resonance imaging (MRI) or transabdominal ultrasonography.

### **Inclusion criteria**

- 1) Aged 18-70 year;
- 2) Onset of pancreatitis within 2 weeks;
- 3) Complicated with gastrointestinal failure, which was defined if the patients were complicated with obvious abdominal distention, abdominal rumbling sound weakening or disappearance, no self-defecation as well as intra-abdominal hypertension (IAH).

### **Exclusion criteria**

- 1) Complicated by gastrointestinal bleeding or intestinal fistula;
- 2) Pregnancy and lactation women;
- 3) Not signed the informed consent;

- 4) Diabetes and autoimmune disease;
- 5) Multiple organ failure, which was defined as two or more organ failure including respiratory failure, renal failure or circulatory failure, which was defined as a score of 2 or more using the modified Marshall scoring system^17.

### **Sample size**

To detect a minimal clinically relevant difference of 35% between FMT group and control group in the primary outcome, and estimating that FMT would achieve 85% power and control would achieve 50% power and using a type I error of 0.05 and a type II error of 0.20 (80% power), we calculated that a minimal sample size of 48 with 24 patients in each group was required. To allow for dropouts, we included 60 participants with 30 in FMT group and 30 in control group.

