### **Randomization and masking**

A randomization sequence for 60 participants with an allocation ratio of 1:1 was generated using SPSS by an independent statistician who not involved in the clinical performance of the trial. The method of allocation concealment was sequentially numbered sealed opaque envelopes technique. Each participant got a study number at enrolment. An allocator (non-study personnel) then allocated participants to FMT or control group by the randomization sequence. This was done in a closed room and the allocation sequence were immediately disposed of. Investigators, patients and outcome assessors were kept masked to the allocation. The randomization key was revealed to researchers when all participants completed the 6-month follow-up and data analysis was completed.

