### **Microbiomics analysis**

Fecal samples were longitudinally collected from patients at baseline before first FMT, one weeks and two weeks after first FMT. The fresh feces were collected in sterile cryopreservation tube by the nurses and kept at -20 °C immediately. Then, the feces were transferred within 6 hour after a bowel movement, and were stored at -80 °C until DNA extraction.

Bacterial DNA was extracted from fecal samples using the E.Z.N.A. Soil DNA Kit (Omega Bio-Tek, Norcross, GA, USA) according to the manufacturer's instructions. The final DNA concentration and purification were determined by NanoDrop 2000 UV-vis spectrophotometer (Thermo Scientific, Wilmington, USA), and DNA quality was checked by 1% agarose gel electrophoresis. The V3-V4 hypervariable regions of the bacteria 16S rRNA gene were amplified with primers 338F (5'-ACTCCTACGGGAGGCAGCAG-3') and 806R (5'-GGACTACHVGGGTWTCTAAT-3') by thermocycler PCR system (GeneAmp 9700, ABI, USA). The PCR reactions were conducted using the following program: 3 min of denaturation at 95°C, 27 cycles of 30 s at 95°C, 30 s for annealing at 55°C, and 45 s for elongation at 72°C, and a final extension at 72°C for 10 min. PCR reactions were performed in triplicate 20 µL mixture containing 4 µL of 5 × FastPfu Buffer, 2 µL of 2.5 mM dNTPs, 0.8 µL of each primer (5 µM), 0.4 µL of FastPfu Polymerase and 10 ng of template DNA. The resulted PCR products were extracted from a 2% agarose gel and further purified using the AxyPrep DNA Gel Extraction Kit (Axygen Biosciences, Union City, CA, USA) and qualified using QuantiFluro-ST (Promega, USA).

Purified amplicons were pooled in equimolar and paired-end sequenced (2×300) on an Illumina MiSeq platform (Illumina, San Diego, USA). The raw reads were deposited into the NCBI Sequence Read Archive (SRA) database (Accession Number: SRP). The raw reads were demultiplexed and quality-filtered by Trimmomatic and merged by FLASH software. The high-quality sequences were assigned to samples according to barcodes. Operational taxonomic units (OTUs) were clustered with 97% similarity cutoff using UPARSE (version 7.1, <http://drive5.com/uparse/>) and chimeric sequences were identified and removed using UCHIME. The taxonomy of each 16S rRNA gene sequencing was analyzed by RDP Classifier algorithm (<http://rdp.cme.msu.edu/>) against the Siva (SSU123) 16S rRNA database using confidence threshold of 70%.

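### Does the plan need changing because it never says who is in the primary-analysis denominator or how a missing one-week GIF score is counted?

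*Combined protocol and SAP*

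**What the plan says.** In the combined protocol and SAP, Sample size assumes recovery in 85% on FMT and 50% on control, "using a type I error of 0.05 and a type II error of 0.20 (80% power"), and arrives at 24 per arm. It then adds the allowance: "To allow for dropouts, we included 60 participants with 30 in FMT group and 30 in control group". It gives no dropout rate, does not define dropout, and does not say whether dropouts leave the analysis.

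Primary Endpoint reads: "The primary end point was the recovery of gastrointestinal dysfunction assessed by GIF score one week after intervention". It defines the target state: "The normal gastrointestinal function assessed by GIF score means enteral feeding >50% of calculated needs, without FI and IAH". Death, withdrawal and a missing score are not mentioned. Mortality appears under Secondary endpoints as an outcome of its own.

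Statistical analysis offers the chi-square or Fisher test for categorical outcomes and adds: "We estimated relative risks (RRs) and 95% confidence intervals (CIs) for primary outcomes and secondary outcomes". It names no analysis set.

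Two other sections bear on the point. Intervention states: "All participants underwent interventions one day after allocation". Randomization and masking states: "The randomization key was revealed to researchers when all participants completed the 6-month follow-up and data analysis was completed".

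**The concern.** The patients are in intensive care with acute pancreatitis and gastrointestinal failure, so some deaths or losses before one week are plausible, and the sponsor planned for losses. A plan that expects losses would normally say how they count.

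The text seems to point two ways. Inflating 24 to 30 per arm restores the required number only if lost patients are removed from the analysis. Yet recovery requires enteral feeding above a threshold, which a patient who has died cannot meet, so a death kept in the denominator is a non-recovery.

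Two smaller doubts add to this. Two infusions are given, and Primary Endpoint does not say which one starts the week. A patient randomised but never infused would have no defined assessment date.

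At stake are the primary relative risk, its p value and the power that 60 patients provide.

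**Working it through.** **Inputs.** 85% versus 50%, type I error 0.05, 80% power, 24 then 30 per arm (Sample size); two-sided testing by chi-square or Fisher (Statistical analysis). The share of patients without a one-week score is not given. I take 1 in 30 to 20% per arm, the top being the allowance implied by 1 − 48/60.

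**The plan's own figures.** With unpooled variance, n = (0.85×0.15 + 0.50×0.50) × (1.96 + 0.84)² / 0.35², which with unrounded normal quantiles is 24.19 per arm, stated as 24. The allowance is 24/0.80 = 30 per arm, or 48/0.80 = 60. The same total comes from 48 × 1.25, so exclusion of dropouts is an inference from the arithmetic, not something the section says. Exact power of the uncorrected chi-square test is 76.7% at 24 per arm and 84.7% at 30.

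**Effect of the denominator.** Assume that missingness is equal between arms and unrelated to recovery. If q is the missing share, counting the missing as not recovered changes the rates to 0.85(1 − q) and 0.50(1 − q) on 30 per arm. Leaving them out keeps the rates and shrinks the arms. The last column is from simulation.

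| Missing per arm | Power, left out | Power, counted not recovered | Rules disagree on significance |
|---|---|---|---|
| 1 of 30 | 83.9% | 80.2% | about 6% of trials |
| 5% | 83.2% | 78.0% | about 8% |
| 10% | 81.3% | 71.7% | about 14% |
| 20% | 76.4% | 60.1% | about 22% |

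Unequal losses also move the estimate. If 4 FMT and no control patients are lost, the difference is 35 points among completers and 0.85×26/30 − 0.50 = 23.7 points on 30 per arm.

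**Deaths on their own.** If early deaths fall among patients who would not have recovered anyway, keeping them in as non-recoveries leaves the rates at 85% and 50% and power at 84.7%. For deaths, the rule that follows from the endpoint definition then costs nothing.

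**Example tables (chi-square p, then Fisher p).**
- Deaths left out, 22/28 versus 15/29: RR 1.52, p = 0.034; 0.052.
- Deaths kept, 22/30 versus 15/30: RR 1.47, p = 0.063; 0.110.
- Missing left out, 20/24 versus 12/24: RR 1.67, p = 0.014; 0.030.
- Missing counted as not recovered, 20/30 versus 12/30: RR 1.67, p = 0.038; 0.069.

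The first pair crosses 0.05 only under chi-square and the second only under Fisher. Expected counts exceed 5 throughout, so chi-square would be the usual choice. The examples are constructed to lie near the boundary.

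**Do the sections conflict?** No. Deaths can count as non-recovery while other dropouts are excluded, and both sections are then satisfied.

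**Start of the week.** Secondary endpoints times the stool samples from the intervention. Microbiomics analysis times the same samples "one weeks and two weeks after first FMT". The intervention therefore most naturally means the first infusion, and Primary Endpoint uses the same term.

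**Never infused.** Intervention says that all participants were treated the day after allocation. No section describes an uninfused patient.

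**The case for a change.** The best case for a change is that the gap is real and cheap to close. One sentence naming all randomised patients, with death as non-recovery and one rule for missing scores, would settle it, and the primary result can depend on it. Masking is also less secure than it looks: the Introduction and Methods call the trial single-blind, whereas Randomization and masking says that investigators and outcome assessors are masked too.

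The omission stands, and so do the power figures. The rest is weaker. The sentence on death would only restate what the definition of recovery implies once the patient is in the denominator.

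The open part is the living patient without a score, and there no rule is plainly better:
- Carrying forward the last recorded status brings its own bias. It may also be unavailable, since intra-abdominal hypertension needs two pressure readings 1 to 6 hours apart and no section schedules one at discharge.
- Imputation within arms of 30 is one option among several.
- Counting such patients as not recovered would need about 37 per arm at 10% missing, and 48 at 20%, to hold 80% power. If 20% of recovered FMT patients and 10% of recovered control patients left early without a status, power would be 44%, against 77% with them left out.

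The remark about blinding concerns a different inconsistency. The explicit statement remains that the key is withheld until the data analysis is complete, which limits choosing a denominator by its result.

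**Conclusion.** No change to the plan follows. The documents omit the analysis set and the missing-score rule, but they state nothing wrong on this point and do not contradict themselves. A competent analyst would keep patients in their allocated arm, count early deaths as not recovered and report how many scores were missing in each arm. Nothing in the plan stands in the way.

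The consequence depends on a loss rate that the documents do not give. At 1 of 30 missing per arm the two extreme rules differ by about 4 points of power (84% against 80%), and at 10% by about 10 points (81% against 72%). The 16-point gap at 20% (76% against 60%) assumes that the whole implied allowance is used within one week. Two features make that an upper scenario: multiple organ failure is excluded at entry, and patients are followed throughout their hospital stay. All these figures assume 85% versus 50%, the chi-square test, and equal missingness unrelated to recovery. Large or unequal one-week losses would make the reported denominators deserve close reading, but nothing in the documents indicates them.
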